2.8.1.1 Adverse events of special interest / grouping of AEs

Safety topics of interest, such as risks defined in the Risk Management Plan (RMP), are defined in the Case Retrieval Sheet (CRS) that is stored in CREDI. For the evaluation of RMP risks, primary and secondary MedDRA SOCs will be considered.

2.8.2 Deaths

Deaths – including on treatment and post treatment deaths – will be listed by treatment group including the start date of the study treatment, the last date on study treatment, the death date and the reason for death. Deaths from the on-treatment period will be flagged.

2.8.3 Laboratory data

All laboratory data (hematology, clinical chemistry, urinalysis and thyroid-related parameters) from the on-treatment period will be listed by treatment group, patient, and visit/time and if normal ranges are available abnormalities will be flagged. Summary statistics for clinical notable laboratory values will be provided by treatment and visit.

The following clinical notable laboratory values are defined:

Liver function and related variables	
ALT (SGPT)	> 3 × ULN
AST (SGOT)	> 3 × ULN
Total bilirubin	> 2 × ULN
Alkaline phosphatase	> 2 × ULN
Renal function and electrolyte variables	
Creatinine (serum):	> 1.5 × ULN
Hematology variables	
Hemoglobin	≥ 20 g/dL decrease from Baseline
Platelet count	< LLN
White blood cell count:	< 0.8 × LLN
Neutrophils	< 0.9 × LLN
Eosinophils	> 1.1 × ULN
Lymphocytes	> 1.1 × ULN
Urinalysis variables	
Protein urine dipstick	++* (* ++ is ≥ 100 mg/dL)

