#### **Clinical laboratory evaluations**

All laboratory data will be listed by treatment group, patient, and visit/time and if normal ranges are available abnormalities will be flagged. Summary statistics will be provided by treatment and visit/time.

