2.1 Data analysis general information

The data will be analyzed by Novartis and/or a designated clinical research organization (CRO). Any data analysis carried out independently by the investigator should be submitted to Novartis before publication or presentation.

Statistical analysis of all data will be performed using SAS[®] statistical software (SAS Institute, Cary, NC, USA) version 9.4 or higher.

General descriptive statistical rules

Categorical data will be presented as frequencies and percentages. In general, missing values are not considered for calculation of percentages (i.e., adjusted percentages are calculated) if not otherwise specified.

For continuous data, the number of non-missing observations, mean, standard deviation, median, minimum, and maximum will be presented.

Unless otherwise stated, summary tables/figures/listings (TFLs) will be presented for each treatment arm in the respective analysis set.

General information on treatment arm handling, decimal places and other output-related information will be specified in TFL shells accompanying this analysis plan.

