2.8 Safety analyses

Summaries may be performed separately for initial (Baseline to Week 16) period and entire study period (including follow-up). Week 16 is chosen due to the fact that patients may be switched to another treatment at this time. Use of data up to and including the last visit before first switch opportunity provides an unbiased comparison between AIN and placebo; data collected beyond Week 16 are included in analyses which summarize the entire study period.

All listings and tables will be presented by treatment group. Safety summaries include only data from the on-treatment period and follow-up period with the exception of Baseline data that will also be summarized where appropriate (e.g., change from Baseline summaries). The on-treatment period is defined as date of first treatment to (date of last treatment + 84 days).

In addition, a separate summary for death including on-treatment and post-treatment deaths will be provided.

In particular, summary tables for AEs will summarize only on-treatment events, with a start date during the on-treatment period (treatment-emergent AEs) for the DBTP and the entire study period.

Missing data will not be imputed for safety endpoints.

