2.8.1 Adverse events (AEs)

In the frame of safety analysis the following treatment-emergent AE types will be considered:

- Any AE
- Study treatment related AE
- AE leading to study treatment discontinuation
- Serious AE (SAE)
- Study treatment related SAE
- SAE leading to study treatment discontinuation
- Death

- RMP risks

All AE tables will be summarized by treatment group.

The Medical Dictionary for Regulatory Activities (MedDRA) version 24.0 or later will be used to code all AEs to a system organ class (SOC) and a preferred term (PT).

An overview table of the number and percentage of patients having each type of AE will be given. Crude incidence and exposure adjusted incidence rates will be provided (see [Section 5.4.3](#) [safety analysis]).

Tables with number and percentage of patients having particular AE summarized by treatment group, SOC and PT will be provided for all AEs listed above except for death. Summaries will be provided for each AE type separately.

For AE type ‘any AE’ tables with number and percentage of patients having particular AE summarized by treatment group, SOC, PT and maximum severity will be provided.

The SOCs will be presented in the alphabetic order and PTs will be ordered within the SOCs by decreasing order of frequency in the secukinumab treatment group.

If a patient reported more than one AE with the same PT, the AE with the greatest severity will be presented. If a patient reported more than one AE within the same primary system organ class, the patient will be counted only once with the greatest severity at the system organ class level, where applicable.

All AEs, deaths, SAEs and AEs leading to permanent treatment discontinuation and leading to study discontinuation and AEs related to COVID-19 will be listed separately. In addition an ocular AE listing with laterality will be provided.

Table 2-4 Overview of analyses on some safety endpoints

Analysis period	AEs & SAEs	AEs by maximum severity	Study treatment related AEs	Notables for vitals, lab criteria
Day 1 – Week 16	•Crude incidence	•Crude incidence	•Crude incidence	•Crude incidence
Entire study phase	•Crude incidence Exposure time adjusted incidence	•Crude incidence	•Crude incidence	•Crude incidence

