2.8.4.2 Vital signs

Notable vital signs abnormalities will be analyzed by treatment group for the DBTP and the entire study period. A frequency table will be provided.

Normal blood pressure will be defined as systolic blood pressure (SBP) of 90 to < 120 mmHg, and diastolic blood pressure of 60 to < 80 mmHg under the measurement conditions outlined in the protocol. Notable blood pressure findings will be hypertension (SBP of ≥ 140 mmHg and/or diastolic blood pressure [DBP] of ≥ 90 mmHg) or hypotension (SBP of < 90 mmHg and/or a DBP of < 60 mmHg).

A normal pulse rate will be defined as a rate of 60 to 100 beats per minute (bpm). Notable pulse rate abnormality will be a rate below 60 bpm (bradycardia) or above 100 bpm (tachycardia).

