2.14 Interim analysis

Due to premature study discontinuation, no interim analysis is planned.

3 Sample size calculation

A final number of 28 patients is expected to be randomized by the time of study discontinuation. Therefore, all analyses will be performed and interpreted in a purely descriptive manner.

4 Change to protocol specified analyses

Due to premature study discontinuation, purely descriptive analyses will be performed for primary and secondary endpoints. Exploratory endpoints will not be analyzed.

5 Appendix

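### Minor safety-reporting point: the notable-hemoglobin criterion (a fall of at least 20 g/dL) can practically never be met, and SAP 2.8.3, on its likelier reading, narrows the protocol's laboratory summaries without recording the change

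*SAP*

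**What the plan says.** **Protocol.** Section 12.5.2, under clinical laboratory evaluations, plans a listing of all laboratory data and then adds, without restriction: "Summary statistics will be provided by treatment and visit/time". Section 8.4.1 names the hematology and chemistry tests. Appendix 1 defines notable values; for hemoglobin the criterion is a decrease from Baseline of 20 g/dL or more. Exclusion criterion 24 bars patients with hemoglobin under 8.5 g/dL at Screening.

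**SAP.** Section 2.8.3 keeps the listing: "All laboratory data (hematology, clinical chemistry, urinalysis and thyroid-related parameters) from the on-treatment period will be listed by treatment group, patient, and visit/time", with abnormal values flagged where normal ranges exist. For summaries it says: "Summary statistics for clinical notable laboratory values will be provided by treatment and visit". It then gives 12 criteria, including the same hemoglobin criterion. Table 2-4 in Section 2.8.1 covers laboratory data only under the column "Notables for vitals, lab criteria", as crude incidence. Section 2.8 refers in general terms to "Baseline data that will also be summarized where appropriate (e.g., change from Baseline summaries", without naming laboratory data. Section 4, the place for departures from the protocol, states only that "purely descriptive analyses will be performed for primary and secondary endpoints. Exploratory endpoints will not be analyzed".

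**The concern.** The two parts have different origins. The hemoglobin criterion is an error within the definition itself, carried unchanged from the protocol into the SAP. A criterion that no patient can realistically meet produces a row of zeros, which a reader may take as evidence that hemoglobin did not fall.

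The second part is a difference between the documents. The protocol planned a descriptive comparison of laboratory values by arm and visit. The SAP appears to replace it with counts of patients beyond fixed cut-offs and does not record this as a change. Early termination does not explain it, because the planned laboratory summaries were already descriptive. At stake is the ability to see shifts between arms that stay short of a cut-off. Neutrophils are the clearest case: Protocol 4.5 names neutropenia as an observed risk and says patients on anti-thyroid medication may be at higher risk. The SAP specifies one neutrophil cut-off, below 0.9 times the lower limit of normal.

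**Working it through.** **Part 1: the hemoglobin criterion**

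Inputs: criterion, a fall of at least 20 g/dL (SAP 2.8.3; Protocol Appendix 1); entry limit, 8.5 g/dL (Protocol 5.2, criterion 24). The documents give no Baseline distribution, so I assume 12 to 16 g/dL.

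- Hemoglobin cannot go below zero, so a fall of 20 g/dL needs a Baseline of at least 20 g/dL, which is 20 / 8.5 = 2.35 times the entry limit.
- A patient who ended at 8.5 g/dL would have had to start at 8.5 + 20 = 28.5 g/dL to count as notable.
- Fall to 8.5 g/dL, and its share of the criterion:

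| Assumed Baseline (g/dL) | Fall to 8.5 (g/dL) | Share of 20 g/dL |
|---|---|---|
| 12 | 3.5 | 17.5% |
| 14 | 5.5 | 27.5% |
| 16 | 7.5 | 37.5% |

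None of these falls reaches the criterion. If 20 g/L was meant, which is an assumption, the criterion is 20 / 10 = 2 g/dL, and all three falls would count.

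**Part 2: what is still summarized**

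The reading of SAP 2.8.3 comes first. The protocol's summary sentence has no qualifier; the SAP's corresponding sentence adds one. Table 2-4 fits the narrower reading, since it shows laboratory data only as notables. Where the SAP wants ordinary by-visit summaries it says so directly: Section 2.6.2 for the secondary endpoints and Section 2.11 for GO-QoL. Vital signs follow the same pattern: the protocol plans summary statistics by arm and visit, while SAP 2.8.4.2 gives notable abnormalities and says "A frequency table will be provided".

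On that reading, the count is:

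- Hematology tests in Protocol 8.4.1: 5 + 6 in the differential = 11.
- Chemistry tests in Protocol 8.4.1: 25. Total 11 + 25 = 36.
- SAP criteria on these tests: 6 hematology (hemoglobin, platelets, white cells, neutrophils, eosinophils, lymphocytes) + 5 chemistry (ALT, AST, total bilirubin, alkaline phosphatase, creatinine) = 11. The twelfth criterion, urine protein, lies outside the 36.
- Tests with no specified post-Baseline summary: 36 - 11 = 25.

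Section 4 mentions primary, secondary and exploratory endpoints. The secondary safety endpoint in SAP Table 1-1 is adverse-event frequency, so Section 4 does not cover laboratory summaries.

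**The case against.** The strongest reply is that little is lost. All on-treatment laboratory values are listed by arm, patient and visit, with abnormalities flagged. Clinically significant laboratory abnormalities are recorded as adverse events (Protocol 10.1.1) and so reach the tables by system organ class, preferred term and severity, and the RMP-risk tables. Protocol Appendix 1 ties no predefined action to a notable value, so the hemoglobin criterion does not drive patient management. All of this stands, and it is why the point is minor.

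The SAP sentence can also be read less strictly: summary statistics by visit is loose wording for notable values, and Table 2-4 covers only some safety endpoints and is organized by period, not by visit. In addition, SAP 2.1 says that output-related details "will be specified in TFL shells accompanying this analysis plan", and those shells are not in the public text. This also stands: the narrow reading is likelier but not certain, and the tables may already be planned.

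A reader might infer four stronger claims that the documents do not support:

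- **A large hemoglobin fall would go unnoticed.** It would be missed by the notable count, but the listing flags abnormal values where a normal range exists.
- **The protocol firmly planned change from Baseline for every test.** Section 12.5.2 offers change-from-Baseline summaries only as an example, where appropriate, and SAP 2.8 keeps that wording.
- **Thyroid summaries were dropped.** The thyroid row of Protocol 8.4.1 is missing from the public text, so nothing can be concluded; thyroid tests are not counted here.
- **25 of 36 measures harm.** It is an unweighted count that treats uric acid like any other test.

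**Conclusion.** Both parts hold as minor points. The hemoglobin criterion is wrong as written in both documents; that conclusion needs no assumption beyond hemoglobin being far below 20 g/dL in practice. What value was intended is unknown.

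The narrowing of the laboratory summaries rests on the likelier reading of SAP 2.8.3 and on the shells not already restoring the tables. Given both, 25 of 36 named hematology and chemistry tests have no specified post-Baseline summary, the other 11 are tabulated at one cut-off each, and the change is unrecorded. The effect on the safety conclusion cannot be quantified from the documents. With 28 patients randomized, full on-treatment listings and intact adverse-event tables, it is probably small. The inconvenience is that a reader who wants the size of laboratory shifts by arm must work from listings.

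**What to change.** 1. **Hemoglobin.** Check the value and unit in SAP 2.8.3 and Protocol Appendix 1 and correct both. If 20 g/L was intended, the criterion becomes a fall of at least 2 g/dL.
2. **Laboratory summaries.** State in SAP 2.8.3 that hematology values (including neutrophils and hemoglobin) and clinical chemistry values will be summarized descriptively for each arm at each visit, citing Protocol 12.5.2. Change from Baseline can be added under the general wording of SAP 2.8, but should not be attributed to 12.5.2 as a firm plan. If the narrower output is preferred, record it with a reason in SAP Section 4.
3. **Shells.** If they already contain these tables, only the SAP wording needs to change.

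Cost: one or two sentences, a corrected criterion in both documents and a few descriptive tables from data already held. No new visits, samples or patients are needed. The downside is extra output with small cells at 28 patients, for description only.

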- 21. Active systemic infections during the last 2 weeks (exception: common cold) prior to randomization or any infection that reoccurs on a regular basis.
- 22. History of an ongoing, chronic or recurrent infectious disease, or evidence of tuberculosis infection as defined by a positive QuantiFERON TB-PLUS test (QFT) at Screening. Patients with a positive or indeterminate QFT test may participate in the study if full tuberculosis work up (according to local practice/guidelines) was completed within 12 weeks prior to randomization and establishes conclusively that the patient has no evidence of active tuberculosis. If presence of latent tuberculosis is established, then treatment must have been initiated and maintained according to local guidelines prior to randomization.
- 23. Significant medical problems, including but not limited to:
  - Congestive heart failure (New York Heart Association status of class III or IV).
  - Severely reduced kidney function (estimated glomerular filtration rate (eGFR)  $\leq$  29 mL/min/1.73 m^2).
  - Uncontrolled diabetes (Type I or Type II) defined as  $HbAlc \ge 10\%$  at Screening.

- 24. Total white blood cell (WBC) count < 3000/μL, or platelets < 100 000/μL or neutrophils < 1500/μl or hemoglobin < 8.5 g/dl at Screening.
- 25. History of clinically significant liver disease or liver injury indicated by abnormal liver function tests, such as serum glutamic oxaloacetic transaminase (SGOT) (aspartate aminotransferase (AST)), serum glutamic pyruvic transaminase (SGPT) (alanine aminotransferase (ALT)), alkaline phosphatase and serum bilirubin. The investigator should be guided by the following criteria:
  - SGOT (AST) and SGPT (ALT) may not exceed 3 × the upper limit of normal (ULN). A single parameter elevated up to and including 3 × ULN should be re-checked once more as soon as possible, and in all cases, at least prior to randomization, to rule-out laboratory error.
  - Alkaline phosphatase may not exceed 2 × ULN. An elevation up to and including 2 × ULN should be re-checked once more as soon as possible, and in all cases, at least prior to randomization, to rule-out laboratory error.
  - Total bilirubin may not exceed 2 × ULN. If the total bilirubin concentration is increased above 2 × ULN, total bilirubin should be differentiated into the direct and indirect reacting bilirubin.

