- Dose not changed
- Dose reduced/increased
- Drug interrupted/withdrawn

6. Its outcome (i.e., recovery status or whether it was fatal).

Conditions that were already present at the time of informed consent should be recorded in medical history of the patient.

Adverse events (including laboratory abnormalities that constitute AEs) should be described using a diagnosis whenever possible, rather than individual underlying signs and symptoms.

Adverse event monitoring should be continued for at least 30 days following the last dose of study treatment in case of early study discontinuation, preferably a follow-up visit or contact 12 weeks after last study treatment should be performed.

Once an AE is detected, it must be followed until its resolution or until it is judged to be permanent (e.g., continuing at the end of the study), and assessment must be made at each visit (or more frequently, if necessary) of any changes in severity, the suspected relationship to the interventions required to treat it, and the outcome.

Information about adverse drug reactions for the investigational drug can be found in the IB.

Abnormal laboratory values or test results constitute AEs only if they fulfill at least one of the following criteria:

- They induce clinical signs or symptoms
- They are considered clinically significant
- They require therapy

Clinically significant abnormal laboratory values or test results must be identified through a review of values outside of normal ranges/clinically notable ranges, significant changes from baseline or the previous visit, or values which are considered to be non-typical in patient with the underlying disease. Alert ranges for laboratory and other test abnormalities are included in Appendix 1.

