# 16 Appendices

## 16.1 Appendix 1: Clinically notable laboratory values and vital signs

The following criteria will be used to define expanded limits and notable abnormalities of key laboratory tests. Notable values for blood pressure and pulse are presented in Section 8.4.

No specific action is pre-defined within this protocol to respond to specific abnormal laboratory values, as it will be decided by the Investigator/qualified site staff whether and which specific action needs to be taken to respond to any abnormal values, taking into account the overall status of the patient. For additional information please refer to the laboratory manual.

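### The notable hemoglobin criterion is a fall of at least 20 g/dL, which no patient can realistically have, so its row in the safety table will read zero in both arms

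*SAP*

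**What the plan says.** SAP Section 2.8.3 introduces its list with "The following clinical notable laboratory values are defined". The hemoglobin entry, under hematology, is at least a "20 g/dL decrease from Baseline". Protocol Appendix 1 (Section 16.1) gives the same number and unit, and says of its list: "The following criteria will be used to define expanded limits and notable abnormalities of key laboratory tests".

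The list is used in the analysis and in conduct:

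- SAP Section 2.8.3: "Summary statistics for clinical notable laboratory values will be provided by treatment and visit". Table 2-4 of the SAP also plans crude incidence of notable laboratory values for Day 1 to Week 16 and for the entire study phase.
- Protocol Section 10.1.1, on recognising clinically significant laboratory results: "Alert ranges for laboratory and other test abnormalities are included in Appendix 1". Sections 8.4.1 and 9.1.1 of the protocol also refer to Appendix 1.

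The only other hemoglobin cut-off in the documents is exclusion criterion 24 in Protocol Section 5.2: "hemoglobin < 8.5 g/dl at Screening". It uses the same unit. The notable list has no second hemoglobin criterion, such as an absolute level or a percentage fall.

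**The concern.** A patient can fall by 20 g/dL only if Baseline is at least that high, yet the protocol admits patients from 8.5 g/dL upward. The required fall is more than twice the level at which a patient may still enter (20 / 8.5 = 2.35). The number and the unit cannot both be right.

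At stake is a pre-specified safety output. If the criterion cannot be met, the hemoglobin row shows zero events in each arm whatever happened to the patients. That zero comes from the definition, but in a table it reads as evidence of no effect. It matters more in this SAP than it otherwise would: after early termination with 28 patients randomized, superiority testing has been dropped and the report is descriptive, so the safety tables carry much of what the trial can still say. During conduct, the same line gave investigators an alert range for hemoglobin that could not alert them to anything.

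**Working it through.** The plan states the threshold without deriving it, so there is no figure of its own to reproduce. The check is whether any patient can reach it.

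**Inputs**

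- Threshold: a fall of at least 20 g/dL (SAP 2.8.3; Protocol Appendix 1).
- Lowest hemoglobin at entry: 8.5 g/dL (Protocol 5.2, criterion 24). No upper limit is given.
- Physical limit: hemoglobin must stay above 0.

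**Condition for a flag**

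Baseline - on-study value >= 20, so on-study value <= Baseline - 20.

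| Baseline (g/dL) | On-study value needed (g/dL) | Share of Baseline lost (20 / Baseline) | Possible? |
|---|---|---|---|
| 8.5 | <= -11.5 | 235% | No |
| 10 | <= -10 | 200% | No |
| 12 | <= -8 | 167% | No |
| 14 | <= -6 | 143% | No |
| 16 | <= -4 | 125% | No |
| 18 | <= -2 | 111% | No |
| 20 | <= 0 | 100% | No |
| 21 (assumed) | <= 1 | 95% | Only arithmetically |
| 22 (assumed) | <= 2 | 91% | Only arithmetically |
| 24 (assumed) | <= 4 | 83% | Only arithmetically |

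Every Baseline up to 20 g/dL needs a zero or negative result. Above 20 g/dL, the assumed range of 21 to 24 needs a near-total loss.

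**What the criterion misses.** A patient who goes from 14.0 to 8.0 g/dL has fallen by 6 g/dL. Since 6 < 20, there is no flag. Even a fall from 14.0 to zero would be only 14 g/dL, still short of the threshold.

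**Size of the likely slip (illustration only).** If the figure was meant in g/L, then 20 g/L = 2 g/dL, a factor of 10 smaller, and a Baseline of 14 would be flagged at 12 g/dL or below. A lost decimal point (2.0 printed as 20) would lead to the same fall. The documents state neither reading.

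**Reading fault or redaction?** The same number and unit stand in two separate documents, and neither line shows a gap or blacked-out text. The error is in the plan, and the SAP repeats the protocol's line.

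**The case against.** The strongest reply is that this is one row of one descriptive table, and that hemoglobin remains monitored by other means.

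- SAP Section 2.8.3 lists all laboratory data by patient and visit, and "if normal ranges are available abnormalities will be flagged". The fall from 14.0 to 8.0 g/dL would be listed, and flagged if it lies outside an available normal range.
- Protocol Section 10.1.1 lets an investigator recognise a significant result from normal ranges or from a marked change since Baseline or the previous visit, as well as from the notable ranges. Appendix 1 ties no pre-defined action to any value.
- No test, estimand or stopping rule depends on the row, and anemia is not among the observed risks named in Protocol Section 4.5.
- The word never is slightly too strong, because the protocol sets no upper limit on Baseline hemoglobin.
- The cause is not documented: either the unit or the number could be wrong.

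All of this is correct, and it limits the harm: patient monitoring is not disabled. It does not rescue the row. A normal-range flag in a patient listing is not a comparison between arms, and the summaries that SAP Section 2.8.3 promises by treatment are of notable values only. The point about a very high Baseline has no practical weight. The point about cause does bear on the remedy: the sponsor has to establish whether the number or the unit is at fault.

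**Conclusion.** The criterion is wrong as written in both documents. For any Baseline up to 20 g/dL it cannot be met, by arithmetic alone. For an assumed Baseline of 21 to 24 g/dL it would need a loss of 83% to 95% of all hemoglobin. In practice the sensitivity of the notable-value criterion for hemoglobin is 0%, and its row will read about 0% in both arms in both analysis periods. A true hemoglobin signal cannot appear there.

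The conclusion rests only on the printed threshold and on hemoglobin being positive; it needs no assumption about what was intended. It covers the notable-value summaries and the Appendix 1 alert range, and does not extend to the listings or to adverse event reporting. The most plausible explanations are a g/L figure printed with g/dL or a lost decimal point, but that is inference.

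**What to change.** The sponsor should check the intended hemoglobin number and unit against the laboratory manual, then correct the line in SAP Section 2.8.3 so that the two agree. This must be done before the notable-value tables are run. The change should be recorded in SAP Section 4, because it departs from the protocol's list. The program that derives the flag should be checked to confirm that Baseline, on-study values and threshold are all in one unit.

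Protocol Appendix 1 carries the same error and has to be reconciled. A formal change there needs a written amendment under Protocol Section 14.1. As the trial has ended early, the SAP correction is what the analysis needs, and the clinical study report can note the error in Appendix 1.

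The cost is one table line in each document and a rerun of the derivation. Some patients may now be flagged, which is the purpose of the row. If the table has already been produced, its hemoglobin row should be withdrawn and not read as a finding of no events.
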